## Overview

The primary objective of this study is to examine whether the mindfulness mobile application engages adolescents and reduces rumination and subsequent psychopathology. We hypothesized that adolescents in the mindfulness intervention condition would experience a reduction in symptoms of depression, anxiety, and self-injury relative to those in the control group and that this would be accounted for by a reduction in the tendency to ruminate. We test this by using a randomized, controlled design, comparing the intervention group to a control group that uses the same mobile application for EMA but does not receive the mindfulness exercises.

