## Aims of the study and significance

1. To determine whether this intervention may be acceptable and engaging to adolescents.

Participants will report on their satisfaction with the app as well as be offered the opportunity to continue using it during a follow up period beyond the initial intervention period. Their use will be tracked electronically during the 12-week, follow-up period as an indicator of engagement. If the app engages adolescents, it has the potential to be utilized with a large public health impact.

2. To examine whether the intervention reduces state and/or trait rumination and whether this reduction accounts for a reduction in symptoms of psychopathology.

Testing this putative mechanism is an important advancement that has yet to be examined. By comparing the intervention to a control condition, the proposed study will offer a more rigorous test of this research question than the previously completed small pilot studies. Additionally, we will use multiple informants of psychopathology symptoms at pre, post, and follow-up time points, strengthening our outcome measurement. We will also use multilevel modeling to test the effects of state changes in the proposed mechanism and outcomes on trait levels. If the app shows efficacy, it can be tested in a larger trial to determine whether it may be indicated as a wide-scale preventive intervention. If the app reduces rumination, a transdiagnostic risk factor, as hypothesized, it has the potential to prevent many deleterious mental health outcomes.

Mobile applications are needed to address the mental health needs of adolescents. The majority of youth who need treatment for mental health disorders such as depression do not receive it, due to barriers including perceived stigma and inclination toward self-reliance (Gulliver, Griffiths, & Christensen, 2010). Furthermore, the cost of mental health care and lack of available quality care, especially for racial and ethnic-minority individuals, make the

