### **Sample**

We will recruit 150 adolescent girls and boys, ages 12-15. This age range was chosen to capture the developmental period directly preceding increased rates of depression (Hankin et al., 1998), providing an opportune window for prevention. Participants will be recruited through a recruitment letter mailed to students enrolled in grades 7-10 at a large, local, public school district with over 5000 students in our target age range. In order to maximize the potential of targeting the proposed mechanism, we will only enroll adolescents who report at least moderate baseline levels of trait rumination. This will be accomplished through a 2-question phone screen. Once parents verbally consent and the child has verbally assented, we will ask them to respond to two questions from the Children's Response Style Questionnaire (CRSQ; Abela, Brozina, & Haigh, 2002) that assess brooding, a particularly maladaptive aspect of rumination (Treynor, Gozalez, & Nolen-Hoeksema, 2003). The aggregate of these two questions are highly correlated with the full rumination subscale from the CRSQ ( $r = .79$ ,  $p < .01$ ) and have been associated with depressive symptoms and NSSI in previous work by the PI (Hilt et al., 2008). Adolescents who meet the screening criteria (age 12-15, score of 2 or higher on the brooding questions, and physically and cognitively able to use a mobile application) will be invited to participate in the study. Once they provide written consent and assent, they will be randomly assigned to a condition: EMA only or EMA + Mindfulness at a 1:1 ratio (i.e., ~ 75 participants per condition).

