### Questionnaires

At each time point (baseline, post, follow-up 1, follow-up 2), internalizing symptoms will be assessed using multiple informants (adolescent and parent). Additionally, adolescents will self-report on their self-injurious thoughts and behaviors, trait rumination, and trait mindfulness. Finally, parent-reported demographics will be obtained at baseline, and adolescent satisfaction with the application will be obtained at post. Questionnaires will take adolescents approximately 30 minutes to complete and less than 10 minutes for parents. Questionnaires will be completed online using Qualtrics (a survey software platform with secure data storage) except for the demographics form which will be completed on paper to avoid storing any identifying data on the server.

*Internalizing symptoms.* Depression will be assessed using the gold-standard, self-report Children's Depression Inventory (CDI; Kovacs, 1992). This 27-item questionnaire assesses behavioral, cognitive, and physical symptoms of depression and has high reliability and validity ( $\alpha=.88$ ). Anxiety will be assessed using the Multidimensional Anxiety Scale for Children (MASC; March, Parker, Sullivan, Stallings, & Connors, 1997), a 39-item reliable and valid index of anxiety in youth ( $\alpha=.88$ ). It yields a total score along with subscales for physical symptoms of anxiety, harm avoidance, social anxiety, and separation anxiety. Parent-reported internalizing symptoms will be assessed using the 5-item, internalizing subscale from the Pediatric Symptom Checklist (PSC; Jellinek & Murphy, 1988), a widely-used 35-item measure of psychopathology in youth with sound psychometric properties. All of these questionnaires have shown change in response to interventions in previous research.

*Self-injury.* Thoughts and behaviors related to suicide and NSSI will be assessed with the self-report form of the Self-injurious Thoughts and Behavior Interview (SITBI; Nock, Homberg, Photos, & Michel, 2007), a highly reliable and valid assessment tool used with adolescents.

*Rumination.* Trait rumination will be assessed with the rumination subscale from the CRSQ (Abela, Brozina, & Haigh, 2002). This 13-item subscale has demonstrated good reliability and validity ( $\alpha=.88$ ).

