**Specific Aim 2.** Testing of the hypothesis that the intervention will reduce symptoms through the mediating effect of reduced rumination will be accomplished by capitalizing on both trait-level questionnaire data and state-level EMA data. Using trait-level data, an indirect effect model will be tested to examine the effect of condition (EMA-only vs. EMA + Mindfulness) on each outcome (depressive symptoms, anxiety symptoms, parent-reported internalizing symptoms, and self-injury) through the indirect effect of rumination (see Figure 2). These analyses will be accomplished using the PROCESS macro (Hayes, 2013) for SPSS (IBM Corp.) which relies on bootstrapping to generate bias corrected confidence intervals. This approach is particularly well-suited for testing mediation models with relatively small sample sizes. It also allows for the addition of covariates and/or moderators if inclusion of them are warranted. For example, if there are sex differences in rumination and/or symptoms, as is likely based on previous research (e.g., Hilt, McLaughlin, & Nolen-Hoeksema, 2010), sex can be covaried or tested as a moderator of effects (**Exploratory Aim**) using methods described by Preacher, Rucker, and Hayes (2007). Dose can also be examined as a covariate, to test whether variability in use of the mobile application affects outcomes. These indirect effects models will be tested at each time period (post, follow-up 1, and follow-up 2). If the hypothesis is supported for

[figure not shown]

Figure 2. Conceptual indirect effect model. Note that moderators (e.g., sex) may also be included.

the post-intervention time period, it will be helpful to see if effects are maintained at 6 and 12 weeks. If the hypothesis is not supported at the post-intervention period, it will be possible to examine delayed effects at the follow-up time points. For example, the intervention could reduce rumination first and have a delayed effect on symptoms.

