The primary hypothesis can also be examined on a finer-grain time scale using state-level EMA data to test whether a mindfulness exercise results in reduced negative mood immediately or at subsequent time points relative to each person's average level of mood. Relatedly, we can examine whether mindfulness exercises reduce state rumination compared to one's average level of state rumination and if so, test mediation. Similar to the trait-level models, covariates (i.e., between-person factors such as sex, SES, and race/ethnicity) may be included if warranted. These multilevel models will be estimated in Mplus (Muthén & Muthén, 1998-2015) using maximum likelihood estimation with robust standard errors to account for the nested nature of the data. This approach will allow for the examination of between- and within-person variation in outcomes and is consistent with current recommendations for handling missing data (Baraldi & Enders, 2010).

Although rumination is the proposed mediator, we can also test an alternative mechanism, i.e., changes in mindfulness (**Exploratory Aim**). Another mindfulness intervention found that changes in state mindfulness predicted changes in trait mindfulness (Kiken, Garland, Bluth, Palsson, & Gaylord, 2015). Furthermore, there appears to be an inverse relationship between trait mindfulness and depressive symptoms (e.g., Way, Creswell, Eisenberger, & Liberman, 2010). Thus, it is possible that the intervention will improve symptoms by increasing mindfulness, reducing rumination, or both. Both trait- and state-level mindfulness can be included as mediators in the above-mentioned models (Preacher & Hayes, 2008).

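### The questionnaire mediation models prespecify no baseline rumination or symptom scores, and no between-arm test of questionnaire symptoms is named, so an app that lowers only rumination could show a false indirect effect on symptoms

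*Combined protocol and SAP*

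**What the plan says.** Under Statistical Analysis Plan, Specific Aim 2, an indirect-effect model runs from condition through trait rumination to each of four outcomes: depression, anxiety, parent-reported internalizing symptoms and self-injury. It is fitted at post, follow-up 1 and follow-up 2 with bias-corrected bootstrap intervals, giving 4 × 3 = 12 models.

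Covariates are optional: "It also allows for the addition of covariates and/or moderators if inclusion of them are warranted". The examples that follow are sex and dose. For the EMA models the same section adds: "Similar to the trait-level models, covariates (i.e., between-person factors such as sex, SES, and race/ethnicity) may be included if warranted". The Figure 2 image is not available in the text; its caption reads "Conceptual indirect effect model. Note that moderators (e.g., sex) may also be included".

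The baselines exist. The Aims section promises that "we will use multiple informants of psychopathology symptoms at pre, post, and follow-up time points", and the Questionnaires section collects trait rumination and self-injury on the same schedule, baseline included.

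The Overview hypothesises that adolescents given the intervention "would experience a reduction in symptoms of depression, anxiety, and self-injury relative to those in the control group". The only between-arm tests that the analysis plan names are t-tests of app use and satisfaction. Its comparison on all study variables is of completers with dropouts, not of arms, and the EMA models concern momentary mood and state rumination. The plan does not say whether post or change scores are modelled, or from which wave the mediator is taken.

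**The concern.** Condition is randomised; rumination is not. Randomisation therefore protects the condition-to-rumination path but not the rumination-to-symptom path. The Background itself describes rumination and symptoms as associated, so adolescents who ruminate more will tend to have more symptoms before the app is used. If post scores are modelled without baselines, that older association enters the second path. Multiplied by a real fall in rumination, it gives a non-zero indirect effect even when symptoms did not move.

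Symptom reduction through rumination is the central hypothesis. With no named between-arm symptom test beside it, a significant indirect effect could be reported as a symptom benefit.

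**Working it through.** **Inputs from the documents.** N=150 at 1:1, so 75 per arm; 12 models; bias-corrected bootstrap; correlation .79 between the brooding screen and the full rumination subscale (Sample); reliability .88 for that subscale (Questionnaires); a promise to correct for multiple tests. The plan gives no power calculation to reproduce.

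**Assumed, because the documents give no figures.** Baseline rumination–symptom correlation r = 0.3–0.6; stability of scores over time s = 0.5–0.7; drop in rumination 0, 0.3 or 0.5 SD; two-sided 95% intervals; normal scores.

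**Model with no symptom effect.** R1 = s·R0 − drop·T + e1 and Y1 = s·Y0 + e2, with residual variances 1 − s² and residual correlation c. No path runs from T or R1 to Y1.

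**Large-sample slope of symptoms on rumination, given condition.**
- Post scores, no baselines: s²r + c(1 − s²). With r = 0.5 and c = 0 this is 0.25 × 0.5 = 0.125 at s = 0.5, and 0.49 × 0.5 = 0.245 at s = 0.7.
- Post scores with both baselines: c, which is zero only if nothing after baseline is shared.
- Change scores: with c = 0, (1 − s)²r / [2(1 − s)] = r(1 − s)/2. At s = 0.5 this is 0.25r, the same as for post scores. At s = 0.7 it is 0.15r against 0.49r.

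**Simulated rate at which the interval for the indirect effect excludes zero.** The post-score rows without correction use 1,000 trials per setting and 2,000 bootstrap draws (Monte Carlo error at most 1.6 points). The combined row uses 500 trials per setting, so its low rates are imprecise.

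| Setting | 0.3 SD drop | 0.5 SD drop |
|---|---|---|
| No baselines, c = 0, s = 0.5 | 11–29% | 21–49% |
| No baselines, c = 0, s = 0.6 | 19–44% | 31–74% |
| No baselines, c = 0, s = 0.7 | 27–51% | 48–87% |
| Both baselines, c = 0, s = 0.4–0.8 | 5–8% | 7–9% |
| Change scores, c = 0, s = 0.5 | 10–29% | 17–49% |
| Change scores, c = 0, s = 0.7 | 12–19% | 13–24% |
| c = 0.1, r = 0.5: without / with baselines | 41–50% / 19–24% | 68–87% / 27–29% |
| c = 0.2, r = 0.5: without / with baselines | 50% / 46–60% | 87–90% / 72–74% |
| c = 0.3, r = 0.5: without / with baselines | 52% / 64–76% | 90% / 93–97% |
| No baselines, c = 0, screened, N=120, Bonferroni over 12, s = 0.5 and 0.7 | 0.2–5.2% | 0.6–17.4% |

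The nominal level in the last row is 0.05/12 = 0.4%. Screening uses the .79 correlation with 50–70% of adolescents assumed to pass, which lowers r from 0.3–0.6 to 0.24–0.53. N=120 (20% dropout) and Bonferroni are assumptions.

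**Further checks.**
- With no drop in rumination, the rate without baselines is 1–9% (s = 0.4–0.8).
- With scores at reliability .88, s = 0.6 and c = 0, the rates are 14–40% and 26–66% without baselines, and 5.4–8.1% with them. At c = 0.2 they are 51% and 85% without, 37% and 56% with.
- The baseline-adjusted between-arm symptom test rejects in 4.5–5.0% of trials in every N=150 setting of that set, and in 3.6–6.0% in a separate check.

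**Power of that between-arm test.** Power = Φ(d/SE − z), with SE = √(2/75) × √(1 − ρ²), where ρ is the baseline–outcome correlation. √(2/75) = 0.163, so SE = 0.141 at ρ = 0.5 and 0.117 at ρ = 0.7.
- d = 0.15, ρ = 0.5: Φ(1.06 − 1.96) = 18%; with z = 2.87, 4%.
- d = 0.20, ρ = 0.7: Φ(1.71 − 1.96) = 40%; with z = 2.87, 12%.

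**The case against.** **The plan permits baselines.** True. The covariate sentence is open and sex and dose are examples, so a reader who infers that baselines are excluded goes too far; Figure 2 might even show them. What stands is that they are not prespecified, which leaves a choice across 12 models that could be made after seeing data.

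**The fitted model also estimates condition's direct path.** It does, and software may print a total effect. But the plan names neither as a test and ties no symptom claim to one.

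**The large rates describe a different trial.** This has force. Enrolment is restricted ("we will only enroll adolescents who report at least moderate baseline levels of trait rumination") and multiplicity correction is promised. With screening, N=120 and Bonferroni combined, the per-model rate at a 0.3 SD drop is a few percent at most. It still mostly exceeds 0.4%. The plan's language of reduction could also mean change scores, which lower the inflation at stability 0.7 but not at 0.5.

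**Baselines do not solve it.** Largely right. Three of the four outcomes are adolescent self-reports from the same session as rumination, so a residual correlation of 0.2 or more is plausible. The adjusted rate is then about 45–97% (37% in one setting with measurement error), and adjustment may not help at all. This is a general limit of mediation analysis, and it makes the missing between-arm test the more important gap.

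**The harm is conditional.** It needs a real fall in rumination and no symptom effect. The first is what the trial hopes for; the documents give no figure for either.

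**Conclusion.** The point holds as a prespecification gap with two parts: no baseline score is named in the trait-level models, and no between-arm test of questionnaire symptoms is named. If rumination falls, symptoms do not, and post scores are modelled without baselines, the false indirect-effect rate is above nominal. It is roughly 11–51% (0.3 SD) and 21–87% (0.5 SD) uncorrected, and about 0.2–5% and 0.6–17% per model, against 0.4%, in the combined scenario. These sizes rest on assumed correlations, stability and effects, so the direction is much firmer than the magnitude.

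Three stronger readings are not supported. A reader might infer that the trial will probably report false mediation; without a fall in rumination there is no consistent inflation, and the promised correction shrinks the rates. A reader might infer that adding baselines cures the problem; it does so only if nothing after baseline is shared. A reader might infer that mediation must be barred unless the total effect is significant; the concern requires only that a symptom-reduction claim rest on the randomised comparison.

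**What to change.** 1. Prespecify baseline rumination and the baseline value of the outcome as covariates in both equations of every trait-level model, with post scores as outcomes.
2. Prespecify and report the baseline-adjusted between-arm (total) effect on each symptom outcome at each wave, beside the indirect effect and under the same multiplicity correction. Base any statement that the app reduced symptoms relative to control on that comparison. Describe the indirect effect as evidence on mechanism that assumes no mediator–outcome confounding.
3. State the mediator's wave, using the preceding wave for follow-up outcomes. Add a sensitivity analysis giving the residual rumination–symptom correlation at which the indirect effect would be zero.
4. Label any dose-adjusted model as secondary and non-randomised, because dose is measured after randomisation.

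**Cost.** SAP wording, a few degrees of freedom and some extra analysis; no new data. Adjustment narrows the arm comparison: 1 − √(1 − ρ²) is 13% at ρ = 0.5 and 29% at ρ = 0.7. The real cost is that the symptom-reduction claim will be made less often, since total-effect power is only about 18–40% for a true effect of 0.15–0.20 SD, or 4–12% under Bonferroni over 12. A formal gate on the mediation analysis is not required.

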### **Procedure**

Participants and a parent or guardian will come to the laboratory to provide written assent and consent, complete baseline questionnaires, and get the mobile application and instructions. The lab visit will last approximately 40 minutes. We will put the application on participants' own mobile devices (Android or iOS platform) if they have them and loan mobile devices (Android phones without calling services) to participants who do not have their own. The active intervention period will last three weeks, during which time participants will be

asked to use the application at least three times per day. Undergraduate research assistants (RAs) masked to condition will monitor daily use via the database where responses are logged. Midway through each week of the active intervention period, RAs will send reminder messages for motivation and encouragement. A small bonus (\$5 per week) will be offered to participants for protocol compliance (i.e., using the app 21 times that week). The weekly emails will let participants know whether they were on track to receive the bonus or encourage them to use the app more regularly. At the end of three weeks (i.e., post), participants will be notified to complete questionnaires online. At this time, participants still have the opportunity to use the mobile application, but they will not be reminded to use it so that we can monitor self-motivated use. All use will be monitored electronically through a database that tracks responses with time stamps. After six weeks, participants will again be notified to complete questionnaires online (follow-up 1). Finally, after an additional six weeks (approximately 3 months after post), participants will be notified to complete questionnaires online (follow-up 2) and return borrowed phones if applicable (via drop-off, pick up or mail). The total time that participants' use is monitored will be 15 weeks (i.e., 3 weeks for the active intervention period and 12 weeks of follow up). See Figure 1 for depiction of timeline.

[figure not shown]

Figure 1. Overview of participant activities and compensation.

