### **Statistical Analysis Plan**

**General Analytic Strategies.** The number of participants recruited and retained will be documented, and comparisons will be made on all study variables between those who complete and those who drop out of the study in order to inform external validity. Compliance and intervention dose will be assessed with time-stamped electronic records generated through the app. All data will be inspected for normality and transformations will

be applied as needed. Missing questionnaire data will be handled using multiple imputation if data are missing completely at random (Enders, 2013).

**Specific Aim 1.** There are multiple ways to assess participants' engagement to determine the acceptability of the intervention. The first two involve examining how much adolescents use the mobile application. We will examine compliance during the 3-week intervention period by comparing the amount of application use (as recorded electronically) in the intervention group to the control group. We will also examine use during the follow-up periods (12 weeks), when it is optional. Both of these usage questions can be answered with t-tests comparing use between groups.

The other two ways of measuring acceptability are more direct. Participants will complete a satisfaction questionnaire during the post-assessment, and we will compare scores on these questions between groups using t-tests. Finally, participants in the intervention condition will answer a question after each mindfulness exercise regarding how helpful it was using a 0-100 scale ranging from not at all helpful to extremely helpful. Scores on this question can be averaged and examined separately for each type of mindfulness exercise to see if they fall above the benchmark of 50, indicating that adolescents find them helpful in the moment. With all statistical analyses, we will use best current practices regarding correction for multiple tests.

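### Dose as a covariate in the Aim 2 models cannot show whether use affects outcomes, and a dose-adjusted condition effect is no longer the randomised comparison

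*Combined protocol and SAP*

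**What the plan says.** The base model is stated without dose (Combined protocol and SAP, Statistical Analysis Plan, Specific Aim 2): "Using trait-level data, an indirect effect model will be tested to examine the effect of condition (EMA-only vs. EMA + Mindfulness) on each outcome". Four outcomes at three time points give 4 × 3 = 12 such models, all using both arms. The same paragraph allows covariates and moderators where warranted, and then adds: "Dose can also be examined as a covariate, to test whether variability in use of the mobile application affects outcomes".

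General Analytic Strategies gives the source of dose: "Compliance and intervention dose will be assessed with time-stamped electronic records generated through the app". Specific Aim 1 treats use as a result to be compared by arm: "Both of these usage questions can be answered with t-tests comparing use between groups".

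The Overview says that the control group "uses the same mobile application for EMA but does not receive the mindfulness exercises". Under Mindfulness Intervention, each use in the active arm carries a 67% chance of an exercise, or 85% when the sad or anxious rating is 90 or above. Under Procedure, participants are "asked to use the application at least three times per day" for three weeks, after which use is optional for 12 weeks.

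The plan does not say whether dose means exercises or app sessions, or over which period. It does not confine the dose model to the intervention arm, label it exploratory, or say that the model without dose stays the main result.

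**The concern.** Randomisation balances what exists before allocation. Dose arises afterwards. How often an adolescent opens the app plausibly depends on motivation and distress, which also drive rumination and symptoms. Two things follow.

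- The dose coefficient, which is the stated purpose of the covariate, mixes any effect of use with the reasons for use.
- The condition coefficient beside it is no longer the comparison that randomisation protects. Depending on what dose means, it may answer a different question, be biased, or be unaffected.

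At stake is whether a dose-adjusted null or a dose-adjusted benefit could be reported as the trial's answer on efficacy or mechanism.

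**Working it through.** **The plan's own figure.** There is none to reproduce: the documents give no power calculation and no expected dose effect. For scale, 75 per arm gives 80% power for d = (1.960 + 0.842) × √(2/75) = 0.46, before dropout.

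**Inputs from the documents.** Sample size: "We will recruit 150 adolescent girls and boys, ages 12-15"; allocation: "they will be randomly assigned to a condition: EMA only or EMA + Mindfulness at a 1:1 ratio", so about 75 per arm. Scheduled uses are 3 × 21 = 63. Expected exercises at 63 uses are 63 × 0.67 = 42.2 at the ordinary rate and 63 × 0.85 = 53.6 if every rating were 90 or above. Exercises in controls are 0.

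**Assumptions (not in the documents).** Effect on rumination of 0.46 SD; rumination–symptom path 0.5; mean uses 30, 40 or 50 with SD 15, 12 or 8, capped at 63; 67% chance of an exercise per use; an unmeasured trait correlated +u with rumination and −u with use. There were 4000 simulated trials per setting, with no dropout and a two-sided 5% level. The indirect effect was judged by joint significance of its two paths, not by the plan's bootstrap.

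**1. The dose coefficient.** Suppose use has no effect and is equal in both arms. The trait alone gives a within-arm correlation of use with rumination of −u². The chance of a significant coefficient, by Fisher's z with condition in the model, is about Φ(atanh(u²) × √(150 − 1 − 3) − 1.96), where √146 = 12.08.
- u = 0.3: atanh(0.09) × 12.08 = 1.09; Φ(−0.87) = 19%.
- u = 0.5: atanh(0.25) × 12.08 = 3.09; Φ(1.13) = 87%.

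The nominal rate is 5%. This holds even in the case most favourable to the plan.

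**2. Condition effect, dose = exercises, effect real and acting through exercises.** With exercises in the model, the condition coefficient is the difference between arms at zero exercises, which is zero by construction. Simulation: condition effect on rumination from −0.46 to between −0.005 and +0.023; indirect effect from −0.23 to between −0.002 and +0.012; power from 78–81% to about 5%. Dose correlates 0.82 to 0.97 with arm (variance inflation 3 to 16).

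**3. Condition effect, dose = exercises, effect real but unrelated to dose.** The estimate barely moves (−0.46 to −0.45). Its standard error grows from √(2/75) = 0.163 to about 0.163 × √6.14 = 0.40, and power falls from 80% to 21%.

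**4. Condition effect, dose = exercises, no effect.** With mean use 40 and SD 12, mean exercises are 40 × 0.67 = 26.8 and their variance is 0.67² × 144 + 40 × 0.67 × 0.33 = 73.5. The slope on exercises is −0.67 × 12 × u²/73.5 = −0.109u², so the bias is 0.109 × 26.8 × u² = 2.9u². Simulation: +0.11 (u = 0.2) to +0.74 (u = 0.5), with rejection from 6% to 46%, towards false harm. The mood rule was not simulated. It gives more exercises to distressed participants and so pulls the other way, which means the sign cannot be known in advance.

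**5. Condition effect, dose = app use, no effect, intervention lowers use by s SD.** The bias is about −u² × s. For u = 0.5 and s = 0.8 it is −0.25 × 0.8 = −0.20; for u = 0.3 and s = 0.3 it is −0.09 × 0.3 = −0.03.

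| Arm difference in use (SD) | u | Condition effect, adjusted | Rejection, adjusted |
|---|---|---|---|
| 0.3 | 0.3 | −0.03 | 5.0% |
| 0.3 | 0.5 | −0.08 | 8.3% |
| 0.5 | 0.3 | −0.04 | 5.6% |
| 0.5 | 0.5 | −0.13 | 12.4% |
| 0.8 | 0.3 | −0.07 | 6.6% |
| 0.8 | 0.5 | −0.20 | 20.7% |

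Without dose, rejection is 4.7% to 5.7% in these settings.

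**6. Condition effect, dose = app use, use equal in both arms, real effect.** It is −0.46 with and without dose, and power is 79–82%, even at u = 0.5. There is no bias.

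**The case against.** The strongest reply is that dose is optional. The base model omits it, and nothing says that the dose model replaces the base model. That stands. A reader might infer that the plan's main Aim 2 result is dose-adjusted, or that the trial would report no effect when exercises work; the documents support neither. In step 2 a condition effect near zero is the right answer to the question that model asks, because the dose term carries the effect. The fall in power misleads only someone who reads that coefficient as the effect of assignment.

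A second reply is that the sentence speaks of app use, which exists in both arms, and that the documents do not show use to differ. Procedure gives the same usage request, reminders and bonus without distinguishing arms, and the Aim 1 t-test asks whether use differs without presuming it. This also stands, so it would be too strong to say that adjustment always biases the condition effect. But equal use is something the trial has yet to learn. Also, the intervention group repeats the momentary questions after each exercise, so a count of logged responses would differ by design.

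Third, the indirect effect was never wholly randomised, since the rumination–symptom path is observational with or without dose. Correct: what adjustment costs is the randomised status of the condition paths.

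None of these replies rescues the dose coefficient, which is confounded even when use is equal by arm.

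**Conclusion.** The concern holds in a limited form. As a test of whether variability in use affects outcomes, the covariate fails under either meaning of dose: with no effect of use, the false-positive rate is about 19% to 87% for u of 0.3 to 0.5. The condition effect in a dose-adjusted model is the effect at zero exercises if dose means exercises, biased if dose means app use and use differs by arm, and unbiased if use is equal. With weak confounding (u = 0.3) and app use as dose, the inflation for condition is small, at 5.0% to 6.6%.

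The main conclusion is harmed only if a dose-adjusted model replaces, or is chosen over, the base model. The plan does not intend this in so many words, but it has no rule against it. Effect size, use distribution and confounding strength are all assumptions. The structural facts are in the documents: dose is recorded after allocation, exercises are zero in controls, and the chance of an exercise rises with distress.

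**What to change.** - Remove dose from the covariates of the Aim 2 indirect-effect models, and state that the models by randomised condition without dose are the main result.
- Define dose as exercises completed or as app sessions, and fix the period. Monitoring runs for 3 + 12 = 15 weeks, so a total over all of it would include use after the post assessment.
- Examine dose only in a separate analysis labelled exploratory, for example the association within the intervention arm adjusted for baseline symptoms and rumination, reported as non-causal.
- Optionally add an instrumental-variable estimate of the effect per exercise, with condition as the instrument and the exclusion restriction stated (condition acts only through exercises). With zero exercises in controls it equals the condition effect divided by mean exercises, for example −0.46/26.8 = −0.017 SD per exercise under the assumptions above. It rescales the condition effect and does not test variability in use within the arm, so it does not replace the exploratory analysis.

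The cost is SAP wording and one exploratory model. The dose result will carry a weaker claim.
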